STAR – Statistical Analysis Plan
V3, June 2023

Page 75 of 96

	
 • OR Taking at least one short GC therapy not corresponding to rescue treatment for the entire duration of the study = Yes • OR Taking at least one IV or IM corticosteroid treatment during the protocol = Yes • OR Patient having received at least one corticosteroid infiltration during the protocol = Yes 
" Not if :
 
 • Taking at least one long-term oral corticosteroid during the protocol = No or missing • AND Taking at least one attack corresponding to rescue treatment during the protocol = No or missing • AND Taking at least one short GC therapy not corresponding to rescue treatment for the entire duration of the study = No or missing • AND Taking at least one IV or IM corticosteroid treatment during the protocol = No or missing • AND Patient having received at least one corticosteroid infiltration during the protocol = No or missing
--	---

The proportion of patients supplemented with prednisone will be compared in the two groups using a Chi2 test after verification of the application conditions: theoretical numbers greater than 5. In the event that the application conditions are not respected, an exact test of Fisher will be used.

The significance threshold for the tests is set at 0.05.

STAR – Statistical Analysis Plan
V3, June 2023

Page 76 of 96

5) Proportion of patients who received intra-articular injections

Proportion of patients who required intra-articular or periarticular GC injection during RA-related protocol.

Variable name	Derivations
Intra-articular injections (yes/no)	
From the variables “ Total number of infiltrations received in relation to RA over the duration of post-randomization follow-up ” [Derived variable], we define two modalities:
 
" If yes :
 
 • “ Total number of infiltrations received in relation to RA over the duration of post-randomization follow-up ” ≥ 1 
" Not if :
 
 • “ Total number of infiltrations received in relation to RA over the duration of post-randomization follow-up ” = 0

The proportion of patients having received intra-articular injections will be compared in the two groups using a Chi2 test after verification of the application conditions: theoretical numbers greater than 5. In the event that the application conditions are not respected , a Fisher exact test will be used.

The significance threshold for the tests is set at 0.05.

Off-protocol analysis:

For exploratory purposes, without implementing a statistical test, we will carry out a descriptive analysis of secondary judgment criteria no. 4 and no. 5 in a combined manner.

Variable name	Derivations
Intra-articular injections and Need for short GC salvage treatment (yes/no)	
From the variables “ Need for a short rescue treatment with GC during the protocol ” [Derived variable] and “ Intra-articular injections ” [Derived variable], we define two modalities:
 
" If yes :
 
 • “ Need for short GC salvage treatment during protocol ” = Yes OR • “ Intra-articular injections ” = Yes 
" Not if :
 
 • “ Need for short GC salvage treatment during protocol ” = No AND • “ Intra-articular injections ” = No

The results will be presented using numbers and percentages.

STAR – Statistical Analysis Plan
V3, June 2023

Page 77 of 96

6) Proportion of patients who had at least one relapse during the protocol

Proportion of patients with a flare-up confirmed by the clinician. In the event of flare-up symptoms, the patient will have an additional visit to their center. For DAS28 >3.2, a surge will be confirmed. A flare will also be diagnosed if the DAS28 is >3.2 at any scheduled visit.

Variable name	Derivations
Disease outbreak (yes/no)	
Based on the variables " Has the patient had a flare-up of his illness documented by a doctor (defined by a DAS28 ≥ 3.2) since the last visit? (yes /no) " [CRFp45, p70, p95, p112, p137, p148], we define two modalities:
 
" If yes :
 
 • " Has the patient had a flare-up of his illness documented by a doctor since the last visit? » = Yes to M4 • OR " Has the patient had a flare-up of his illness documented by a doctor since the last visit? » = Yes to M7 • OR " Has the patient had a flare-up of his illness documented by a doctor since the last visit? » = Yes to M9 • OR " Has the patient had a flare-up of his illness documented by a doctor since the last visit? » = Yes to M12 • OR " Has the patient had a flare-up of his illness documented by a doctor since the last visit? » = Yes to ADDITIONAL VISIT 1 • OR " Has the patient had a flare-up of his illness documented by a doctor since the last visit? » = Yes to ADDITIONAL VISIT 2 
" Not if :
 
 • " Has the patient had a flare-up of his illness documented by a doctor since the last visit? » = No or missing at M4 • AND " Has the patient had a flare-up of his illness documented by a doctor since the last visit? » = No or missing at M7 • AND " Has the patient had a flare-up of his illness documented by a doctor since the last visit? » = No or missing at M9 • AND " Has the patient had a flare-up of his illness documented by a doctor since the last visit? » = No or missing at M12 • AND " Has the patient had a flare-up of his illness documented by a doctor since the last visit? » = No or missing at ADDITIONAL VISIT 1 • AND " Has the patient had a flare-up of his illness documented by a doctor since the last visit? » = No or missing at ADDITIONAL VISIT 2

The proportion of patients having had at least one flare-up of the disease (defined by a DAS28 ≥ 3.2) will be compared in the two groups using a Chi2 test after verification of the application conditions: theoretical numbers greater than 5. In the event that the application conditions are not respected, a Fisher's exact test will be used.

7) Area under the curve of the means of the FLARE self-questionnaire at one year

FLARE is an approved self-assessment questionnaire that will be completed at each visit and in case of home FLARE by the patient. Results are expressed as continuous data.

STAR – Statistical Analysis Plan
V3, June 2023

Page 78 of 96

For the analysis of the FLARE doctor questionnaire:

In the ITT population, we will carry out a mixed linear model for repeated data modeling the results of the FLARE questionnaires as a function of the time of administration of the questionnaire (M1 to M12) and the randomization group. We will describe the evolution of the results according to the time of administration of the questionnaire by a graphical representation of these models, in which the time of administration (visit) will be considered as a categorical variable and in which we will take into account a potential interaction between the time of administration and the randomization group.

If the evolution of scores over time is linear and there is no interaction between the time of administration and the randomization group, we will carry out models with the time of administration as a continuous variable (in month). In this case, we will describe the result by estimating a coefficient β with a 95% confidence interval, corresponding to the average difference in scores between the groups between M1 and M12.

If these two conditions are not met (absence of interaction and non-linearity of the relationship), the results of the FLARE questionnaires will be described for each arm at M4 and M7. The difference in distribution between the two arms will be tested using a two-sided Student's test (or a Wilcoxon test if the conditions for applying the Student's test are not verified) for each of these 2 visits. The significance threshold for the tests is set at 0.05.

In the event of missing data on one of the items, the value of the missing item will be replaced by the median value of the item at the visit concerned according to the patient's randomization group.

One approach will be to add up the scores at each time. We will therefore obtain a cumulative sum of the scores. The difference in distribution of the cumulative sums between the two arms will be tested using a two-sided Student's test (or a Wilcoxon test if the conditions for applying the Student's test are not verified) for each of these 2 visits. The significance threshold for the tests is set at 0.05.

In the event of missing data we will use the following imputation methods:

- In the event of missing data on one of the items, the value of the missing item will be replaced by the median value of the item at the visit concerned according to the patient's randomization group.
- In the event of missing data at one or more visits, we will impute the non-missing values of the randomization group from which the patient came at the visit in question by the median value.

Patient FLARE scores should have a large number of missing data (questionnaires poorly completed during follow-up). These scores present will be described in each group using the mean, standard deviation, median and interquartile range. In the event of missing data on one of the items, the value of the missing item will be replaced by the median value of the item at the visit concerned according to the patient's randomization group.

No bivariate analysis will be performed on these scores.

STAR – Statistical Analysis Plan
V3, June 2023

Page 79 of 96

8) Proportion of patients in remission or at low activity level according to the DAS28 at 7 and 12 months

Proportion of patients in remission and with low disease activity at 7 months and one year. Patients with a DAS28 < 2.6 will be considered in remission, patients with a DAS28 between 2.6 and 3.2 will be considered in LDA.

The DAS28 formula is as follows:

$$\text{DAS28} = (0.56 * \text{sqr}(\text{TJC})) + (0.28 * \text{sqr}(\text{SJC})) + (0.7 * \text{ln}(\text{VS})) + (0.014 * \text{GH})$$

Where **TJC** = Number of painful joints [CRFp72, p114]
SJC = Number of swollen joints [CRFp72, p114]
VS = the sedimentation rate [CRFp84, p126]
GH = overall health represents the patient's assessment of disease activity on a scale of 0 to 100 where 100 corresponds to maximum activity [CRFp81, p123].
 The DAS28 is calculated automatically in the e-CRF.

Variable name	Derivations
Remission according to DAS28 (Yes No)	
From the DAS28 scores at M7 and M12 (variable present in the database or programmed), we define two modalities:
 
 • " If yes : 
 ○ DAS28 < 2.6 • " Not if : 
 ○ DAS28 ≥ 2.6 
For each of times M7 and M12, a variable will be created using the same methods.

Low level of activity according to DAS28 (yes/no)	
From the DAS28 scores at M7 and M12 (variable present in the database or programmed), we define two modalities:
 
 • " If yes : 
 ○ DAS28 ≥ 2.6 and < 3.2 • " Not if : 
 ○ DAS28 ≥ 3.2 ○ OR if DAS28 > 2.6 
For each of times M7 and M12, a variable will be created using the same methods.

Remission or low level of activity according to DAS28 (Yes No)	
From the variables " Remission according to DAS28 " and " Low activity level according to DAS28 " [Derived variable], we define two modalities:
 
" If yes :
 
 • " Remission according to DAS28 " = Yes OR • " Low activity level according to DAS28 " = Yes 
" Not if :
 
 • " Remission according to DAS28 " = No AND • " Low level of activity according to DAS28 " = No 
For each of times M7 and M12, a variable will be created using the same methods.

STAR – Statistical Analysis Plan
V3, June 2023

Page 80 of 96

The proportion of patients in remission or at a low level of activity will be compared in the two groups using a Chi² test after verification of the application conditions: theoretical numbers greater than 5. In the event that the application conditions are not not respected, a Fisher exact test will be used.

The significance threshold for the tests is set at 0.05.

STAR – Statistical Analysis Plan
V3, June 2023

Page 81 of 96

9) HAQ-DI score at 4, 7 and 12 months

Functional impairment assessed by the Health Assessment Questionnaire (HAQ) at baseline, 4, 7 months and one year.

The HAQ will be calculated at baseline [CRFp25-26], at 4 [CRFp49-50], 7 months [CRFp74-76] and one year [CRFp116-117], and is expressed as continuous data.

The HAQ-DI SCORE at inclusion 4, 7 and 12 months will be compared in the two groups using a Student t test if the application conditions are met and a non-parametric Mann-Whitney Wilcoxon test otherwise.

The significance threshold for the tests is set at 0.05.

STAR – Statistical Analysis Plan
V3, June 2023

Page 82 of 96

10) RAID score at 4, 7 and 12 months

Patient-reported outcomes assessed by the Rheumatoid Arthritis Impact of Disease (RAID) questionnaire at baseline, 4, 7 months, and 1 year.

The RAID questionnaire will be calculated at baseline [CRFp27], 4 [CRFp51], 7 [CRFp76] and 12 [CRFp118] months and is expressed as continuous data.

The RAID SCORE at inclusion, 4, 7 and 12 months will be compared in the two groups using a Student t test if the application conditions are met and a non-parametric Mann-Whitney Wilcoxon test otherwise.

The significance threshold for the tests is set at 0.05.

STAR – Statistical Analysis Plan
V3, June 2023

Page 83 of 96

11) EQ-5D score at 4, 7 and 12 months

The EuroQol 5-Dimension Descriptive System (EQ-5D) will be completed at baseline [*CRFp31*], at 4 [*CRFp55*], 7 [*CRFp80*] and 12 [*CRFp27*] months. The EQ-5D questionnaire will be calculated at baseline, after 4, 7 and 12 months and is expressed as continuous data.

The EQ-5D scores at inclusion 4, 7 and 12 months will be compared in the two groups using a Student t test if the application conditions are met and a non-parametric Mann-Whitney Wilcoxon test otherwise.

The significance threshold for the tests is set at 0.05.

STAR – Statistical Analysis Plan

V3, June 2023

Page 84 of 96

12) FACIT-F score at 4, 7 and 12 months

Functional Assessment of Chronic Disease Therapy - Fatigue Scale (FACIT-F): The FACIT-F questionnaire explores patient-reported fatigue. It will be completed at baseline [CRFp28-30], at 4 [CRFp52-54], 7 [CRFp77-79] and 12 [CRFp119-121] months. It will be expressed as continuous data.

The responses to the FACIT-F questionnaire at inclusion 4, 7 and 12 months will be compared in the two groups using a Student t test if the application conditions are met and a non-parametric Mann-Whitney Wilcoxon test in the case. opposite.

The significance threshold for the tests is set at 0.05.

STAR – Statistical Analysis Plan
V3, June 2023

Page 85 of 96

13) Proportion of serious adverse events at 1 year

The next secondary outcome is the proportion of patients who experienced at least one serious adverse event over a 1-year period.

Variable name	Derivations
Serious adverse events (yes/no)	
From the tables “ Adverse events 1/3, 2/3, 3/3 ” [CRFp169-171] and the variable “ Severity (serious/non-serious) ” present in these same tables, we define 2 modalities:
 
" If yes :
 
 • Event title is not missing • AND if “G ravité ” = serious 
" Not if :
 
 • Event title is not missing • AND if “G delighted ” = not serious • OR if the event title is missing

Depending on the numbers, the proportion of patients having had one or more serious adverse events can be compared between the two groups using a Chi2 test after checking the conditions of application: theoretical numbers greater than 5. In the case where the conditions applications would not be respected, a Fisher exact test will be used.

The significance threshold for the tests is set at 0.05.

STAR – Statistical Analysis Plan
V3, June 2023

Page 86 of 96

SECURITY ANALYSIS

The population for the safety analysis is composed of all included and randomized patients who received at least one dose of treatment (prednisone and hydrocortisone placebo / Hydrocortisone and prednisone placebo).

Patients will be analyzed in the weaning strategy group actually received (particularly in the event of an error in allocation of treatment and placebo).

All expected or unexpected serious adverse events, and all unexpected non-serious adverse events, occurring from the date of signing the consent, during the duration of the study and until the end of the participant's follow-up provided for by the research (1 year); or up to 24 hours after stopping the experimental treatment (prednisone or hydroxycortisone) in the event of premature exit from the study, will be collected and will be included in an adverse event form after coding according to the dictionary. standardized medical MedDRA.

Adverse events will be described according to the different hierarchical levels of the MedDRA classification. The listing of these adverse events will be presented after grouping into "Preferred Term" and organization by "System-Organ Class". The listing will contain the following information:

- identifier of the subject and center,
- date and time of start of the adverse event,
- date and time of end of the adverse event (or mention of the persistence of the adverse event),
- description of the event ("Reported Term" and "Preferred Term"),
- gravity ,
- attributability to the test or the treatment of the test,
- action on the processing of the test,
- other action and evolution.

Will be presented by arm (prednisone and hydrocortisone placebo / Hydrocortisone and prednisone placebo):

- The incidence of adverse events according to their causality and severity.
- The incidence of adverse events leading to treatment discontinuation.
- Adverse events occurring between signing the consent and the first use of the experimental technique.

STAR – Statistical Analysis Plan
V3, June 2023

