- Subjects who have received glucocorticoid treatment prescribed for an indication other than RA for more than two weeks ,
- Endpoint not determined at the end of the study.

The reasons for excluding the population per protocol will be listed and described in a table.

Patients presenting errors in taking the levels of the treatments under study at M4 [CRF p45] and M7 [CRF p70] were listed and presented to the investigators blinded to the randomization group and therefore to the treatment consumed. The principal investigators then decided, patient by patient, based on the number of capsules consumed per level [Derived variable] and comments from the investigative teams in order to define whether this was a reason for excluding the per population. protocol.

The summary tables (tables 1 and 2) are presented in the appendix to this SAP.

3) Population for safety analysis

The population for the safety analysis will be composed of all subjects included in the study (having given consent to participate and having been randomized), having taken at least one dose of treatment.

Subjects will be analyzed in the treatment group actually received (notably in the event of a batch allocation error).

STAR – Statistical Analysis Plan
V3, June 2023

Page 15 of 96

VARIABLES OF INTEREST

No.	VARIABLE NAME	DERIVATIONS
1	Age at inclusion date (in years)	From the variables “Date of birth” [CRFp9] and “Date of inclusion visit” [CRFp9], we will calculate the number of days, divided by 365.25 to obtain a duration in years. We can convert this duration into months if necessary.
2	Duration of illness at inclusion (in years)	From the variables “Date of RA diagnosis” [CRFp9] and “Date of inclusion visit” [CRFp9], we will calculate the number of days, divided by 365.25 to obtain a duration in years. We can convert this duration into months if necessary.
3	Duration of remission (in years)	From the variable “ Duration of illness (in months) ” [Derived variable] we will subtract the number of months collected by: “How long has the patient been in remission/low activity level?” » [CRFp10]. This will allow us to obtain the duration in years with active disease. We can convert this duration into months if necessary.

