8	Charlson score at baseline	
The Charlson score will be calculated as defined below:
 
 • " History of clinical myocardial infarction " [CRF p14] = Yes then add 1 to the score • " History of decompensation of heart failure " [CRF p14] = Yes then add 1 to the score • " Obliterative arteriopathy of the lower limbs " [CRF p14] = Yes then add 1 to the score • " History of stroke (ischemic or hemorrhagic) " [CRF p14] = Yes then add 1 to the score • " Dementia " [CRF p14] = Yes then add 1 to score 1 • " COPD " [CRF p14] = Yes then add 1 to the score • " History of peptic ulcer " [CRF p14] = Yes then add 1 to the score • " Hepatic pathology " [CRF p14] = Yes 
 ○ AND " Severity " = Mild then add 1 to the score • " History of diabetes " [CRF p14] = Yes 
 ○ AND " Complication " = Not complicated so add 1 to the score ○ AND " Complication " = Complicated then add 2 to the score • " Hemiplegia " [CRF p14] = Yes then add 2 to the score • " Moderate (clearance < 60mL/min) to severe renal impairment (clearance <30mL/min) " = Yes then add 2 to the score • " History of solid cancer " [CRF p14] = Yes 
 ○ AND " Type " = localized then add 2 to the score • " History of Leukemia » [CRF p14] = Yes then add 2 to the score • " History of Lymphoma " [CRF p14] = Yes then add 2 to the score • " Hepatic pathology " [CRF p14] = Yes 
 ○ AND " Severity " = Moderate to Severe then add 3 to the score • "AIDS" [CRF p14] = Yes then add 6 to the score • Age " variable [Derived variable] takes the value: 
 ○ [50 – 60[add 1 to the score

STAR – Statistical Analysis Plan
V3, June 2023

Page 17 of 96

No.	VARIABLE NAME	DERIVATIONS
		
 ○ [60 – 70[add 2 to the score ○ [70 – 80[add 3 to the score ○ [80 – 90[add 4 to the score ○ [90 – 100[add 5 to the score

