The study data will be summarized in descriptive tables. These will contain a column for each type of strategy (A/B). The total number of subjects, including missing observations, will be indicated at the top of each column. The analysis population will be systematically specified in the title of the table.

For continuous variables, the dispersion and central tendency parameters will be used:

- the standard deviation and the mean for Gaussian distributions,
- the interquartile range and the median otherwise.

For categorical variables, the descriptive analysis will be carried out using the numbers and frequencies for each observed modality.

STAR – Statistical Analysis Plan
V3, June 2023

Page 29 of 96

Baseline patient characteristics will be described for the entire ITT population, overall and by randomization group. They will also be described for the PP population if there is a difference in numbers between the ITT and PP population greater than 10%.

Example tables for quantitative variables

	Total (N =...)		Strategy A (N =...)		Strategy B (N =...)	
	Avg	DS	Avg	DS	Avg	DS
	Med	IIQ	Med	IIQ	Med	IIQ

Variable 1*

Variable 2**

* Gaussian distribution variable summarized as mean (Avg), standard deviation (SD)

** Non-Gaussian distribution variable summarized as median (Med), interquartile range [IIQ]

N: total number of subjects (with and without missing data on the variable studied)

n: number of subjects in a given modality of the variable studied

Example Table for Categorical Variables

	Total (N =...)		Strategy A (N =...)		Strategy B (N =...)	
	not	%	not	%	not	%
Variable A						
Modality 1			not	%	not	%
Modality 2			not	%	not	%

N: total number of subjects (with and without missing data on the variable studied)

n: number of subjects in a given modality of the variable studied

Listing of descriptive tables at inclusion

STAR – Statistical Analysis Plan
V3, June 2023

Page 30 of 96

Characteristics of patients at inclusion (ITT population)

- Gender (Male/Female) [CRF p9]
- Age at inclusion (years) [Derived variable]
- Duration of illness (years) [Derived variable]
- Duration of disease in remission/low activity level (months) [CRF p10]

Consumption of alcohol and tobacco:

- Alcohol consumption (yes/no) [CRF p13]
 - Daily consumption (glasses/day) [CRF p13]
- Tobacco consumption (yes/no) [CRF p13]
 - If yes: specify (in progress/withdrawn) [CRF p13]
 - Number of packages/years [CRF p13]
 - Duration of smoking cessation (months) [Derived variable]

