- History of decompensation of heart failure (yes/no) [CRF p14]
- Obliterating arteriopathy of the lower limbs (yes/no) [CRF p14]
- History of stroke (ischemic or hemorrhagic) (yes/no) [CRF p14]
- Dementia (yes/no) [CRF p14]
- COPD (yes/no) [CRF p14]
- History of peptic ulcer (yes/no) [CRF p14]
- History of diabetes (yes/no) [CRF p14]
 - Type of diabetes (Complicated/Uncomplicated) (yes/no) [CRF p14]
- Moderate to severe renal insufficiency (yes/no) [CRF p14]
- Hemiplegia (yes/no) [CRF p14]
- History of leukemia (yes/no) [CRF p14]
- History of lymphoma (yes/no) [CRF p14]
- History of solid cancer (yes/no) [CRF p14]
 - Solid cancer type (Localized/Metastatic) [CRF p14]
- Liver Pathology (yes/no) [CRF p14]
 - Severity of liver pathology (Mild/Moderate to severe) [CRF p14]
- AIDS (yes/no) [CRF p14]
- Osteoporosis (yes/no) [CRF p14]
 - Fracture osteoporosis (yes/no) [CRF p14]
 - Number of severe fractures (yes/no) [CRF p14]
- Osteoporosis treatment (Treated with anti-osteoporosis/Untreated) [CRF p14]
- Other comorbidity associated with RA
 - Precision: ... (yes/no) [CRF p14]
- Charlson Score [Derived Variable]

STAR – Statistical Analysis Plan
V3, June 2023

Page 33 of 96

History and pathologies associated with inclusion (ITT population)

- Presence of FR (yes/no) [CRF p9]
- Presence of ACPA (yes/no) [CRF p9]
- Presence of erosion (yes/no) [CRF p9]
- Presence of extra-articular signs (yes/no) [CRF p9]
- If yes, specify:
 - Cutaneous rheumatoid nodules (yes/no) [CRF p9]
 - Rheumatoid lung (yes/no) [CRF p9]
 - Eye damage related to RA (yes/no) [CRF p9]
 - Felty or pseudo-Felty syndrome (yes/no) [CRF p9]
 - Gougerot-Sjögren syndrome (yes/no) [CRF p9]
 - Amyloidosis (yes/no) [CRF p9]
 - Rheumatoid vasculitis (yes/no) [CRF p9]
 - Others, specify [CRF p9]
- History of orthopedic surgery related to RA (yes/no) [CRF p9]
- If yes, specify:
 - Number of surgical procedures [CRF p 10]
 - Nature of interventions [CRF p10]
- Presence of another inflammatory/autoimmune/dysimmune disease in addition to RA (yes/no) [CRF p 10]
- If yes, specify:
 - Number of associated dysimmune pathologies [CRF p 10]
 - Disease descriptions [CRF p10]

STAR – Statistical Analysis Plan
V3, June 2023

Page 34 of 96

History of disease-modifying treatment for RA (ITT population)

History of disease-modifying treatment for RA

- Background treatment for RA (yes/no) [CRF p11]
- If yes, complete:
 - History of consumption of a synthetic DMARD (yes/no) [Derived variable]

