In the randomized population, those lost to follow-up, that is to say patients for whom the endpoint is missing, will be analyzed as a failure of the strategy (conservative approach). This result will be easy to collect, blindly.

For explanatory variables, descriptive analyzes will be conducted on available data. The number of non-missing subjects (n) will be specified for each explanatory variable.

STAR – Statistical Analysis Plan
V3, June 2023

Page 62 of 96

3) Primary analysis of the primary endpoint (ITT)

The main endpoint will be compared in the two groups using a Chi2 test after verification of the application conditions: theoretical numbers greater than 5. In the event that the application conditions are not respected, a Fisher's exact test will be used.

The significance threshold for the tests is set at 0.05.

STAR – Statistical Analysis Plan
V3, June 2023

Page 63 of 96

4) analysis of the primary endpoint (ITT)

Sensitivity analyses of the primary outcome will include:

- An analysis on complete data (excluding subjects lost to follow-up and with missing data on the primary endpoint) (analysis 1)
- A stratified descriptive analysis (without testing) according to the duration of corticosteroid therapy before inclusion (≤ 2 years or > 2 years) (analysis 2)
- An analysis adjusted for potentially confounding criteria, based on a multiple logistic regression model adjusted for the randomization group as well as the initial characteristics if there is a significant imbalance between the comparison groups regarding the following characteristics (analysis 3):
 - Duration of corticosteroid therapy ≤ 2 years / > 2 years [CRF p19]
 - Duration of remission (in years) [Derived variable]
 - Duration of corticosteroid therapy at 5 mg/day
 - Duration of treatment with prednisone at 5 mg/day (in months) [Derived variable]
 - Age at inclusion date [Derived variable]
 - Sex [CRF p9]
 - Duration of illness on inclusion (in years) [Derived variable]
 - Rheumatoid factors (positive/negative) [Derived variable]
 - Anti-CCP2 (positive/negative) [Derived variable]
 - Presence of erosions [CRF p9]
 - Charlson Index [Derived variable]
 - HAQ score [Derived variable]
 - Synthetic background treatment during the study [Derived variable]
 - Biological background treatment during the study [Derived variable]
 - DAS28 at inclusion [Derived variable]
 - VAS fatigue at inclusion [CRF p16]

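### Sensitivity analysis 3 would use active-disease time under the name of remission, and a Charlson score that gives metastatic cancer no points

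*SAP*

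**What the plan says.** **Remission.** In the SAP's table of variables of interest, row no. 3 is named "Duration of remission (in years". Its derivation starts from the duration of illness, and then "we will subtract the number of months collected by: “How long has the patient been in remission/low activity level". The row goes on: "This will allow us to obtain the duration in years with active disease". The listing of patient characteristics at inclusion contains a different item, taken straight from the CRF: "Duration of disease in remission/low activity level (months) [CRF p10".

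**Charlson.** Row no. 8 of the same table builds the score item by item. For solid cancer the only scoring line is for type "localized then add 2 to the score". The listing of comorbidities shows that the CRF records two types: "Solid cancer type (Localized/Metastatic) [CRF p14".

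**Where they are used.** Part 4 of the primary endpoint section (analysis 3) lists 16 candidate covariates for a logistic regression. One is "Duration of remission (in years) [Derived variable", another is the derived Charlson index, and duration of illness is in the same list. Candidates are considered when the groups differ significantly on them. They are also screened against the outcome at the 0.20 level. The model is fitted only if there are at least 10 successes per variable in it.

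**The concern.** The name and the rule of variable no. 3 contradict each other within one table row. The subtraction and the sentence that explains it agree with each other; only the name differs. A programmer who follows the row produces active-disease time and stores it as remission. Analysis 3 points to this derived variable and not to the CRF item, so the list meant to cover remission does not contain it. It contains instead a quantity that overlaps strongly with duration of illness, another candidate.

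The Charlson rule has a gap where a recorded category receives no points. Taken literally, the more advanced category ranks below the less advanced one and level with no cancer at all.

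At stake are the choice of covariates in analysis 3, the reading of their coefficients, and, for Charlson, also the baseline table. The SAP requires a signed amendment for any deviation, so neither rule can properly be corrected silently during programming.

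**Working it through.** The SAP states no numerical result for either variable, so there is no figure to reproduce. The check applies each rule literally.

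**1. Remission.** Let I be illness duration and R the time in remission or low activity, both in years. The rule gives A = I − R.

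| I | R (true remission) | Coded as remission, I − R |
|---|---|---|
| 10 | 1 | 9 |
| 10 | 2 | 8 |
| 10 | 5 | 5 |
| 10 | 9 | 1 |

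At fixed I, the coded value falls by one year for each extra year of remission. It equals R only when R = I/2.

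**2. Overlap with duration of illness.** The SAP gives no standard deviations, so these figures are illustrations. If I and R are independent, corr(I, I − R) = SD(I) / √(SD(I)² + SD(R)²).

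- SDs of 10 and 2 years: 10/√104 = 0.98.
- SDs of 10 and 5 years: 10/√125 = 0.89.
- Independence is not realistic, because R cannot exceed I. A simulation with I from a gamma distribution (shape 3, scale 4 years) and R as a beta(1.5, 5) fraction of I gave 0.93 with I. The correlation with R was only 0.26.

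The overlap is strong throughout this range, but its exact size is not known. The positive 0.26 also shows that the reversal in step 1 holds at fixed illness duration, not necessarily across all patients.

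**3. Effect on the treatment odds ratio.** If I and A both enter linearly, c·I + d·(I − R) = (c + d)·I − d·R. This is the same model as one with I and R, so the treatment coefficient is identical. The coding matters when variable no. 3 is checked for imbalance or screened on its own, enters without I, or is cut into categories. It also matters when its coefficient is read.

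**4. Room in the model.** With 51 patients per group and success rates of 30% and 60%, expected successes are 51 × 0.30 + 51 × 0.60 = 45.9. If 20% are lost and counted as failures, this becomes 0.8 × 45.9 = 36.7. At 10 successes per variable the model holds 3 or 4 variables including treatment, so 2 or 3 covariates out of 16 candidates. With so few places, a wrong selection has a cost.

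**5. Charlson.** The three graded items in row no. 8 compare as follows.

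| Item | Lower grade | Higher grade |
|---|---|---|
| Diabetes | 1 (uncomplicated) | 2 (complicated) |
| Liver disease | 1 (mild) | 3 (moderate to severe) |
| Solid cancer | 2 (localised) | no line, hence 0 (metastatic) |

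A patient with metastatic cancer scores 2 points below an otherwise identical patient with localised cancer, and the same as one without cancer.

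**The case against.** The strongest reply is that little depends on either error, and most of that stands.

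- **Possibly a naming error only.** The SAP keeps true remission as a CRF item and says openly what the subtraction yields. That fits an active-disease covariate with the wrong name. The document does not settle which was meant, so it cannot be said that the computation rather than the name is at fault. The contradiction remains either way.
- **Remission is not lost from view.** A reader might infer that nobody would notice a group difference in remission. The baseline table describes the CRF months by group, so the loss is confined to the candidate list of analysis 3.
- **The main result is safe.** A reader might infer that the trial's conclusion or the adjusted odds ratio must be distorted. The primary analysis is an unadjusted Chi2 or Fisher test. Analysis 3 is a sensitivity analysis with several conditions, and step 3 of the working shows a case with no effect at all.
- **Units.** The row starts from months and reports years without stating the division by 12. Since it labels the result in years and mentions conversion, this is loose wording and not a second error.
- **Charlson.** This is a missing line, not a stated lower weight. A line lost when the text was extracted cannot be fully excluded, although the items after it (leukaemia, lymphoma, liver disease, AIDS, age bands) are all there. Few or no patients may be affected.

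What the reply does not remove is that two written rules give values that do not match what their names promise, and that both feed a planned analysis.

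**Conclusion.** The point holds in a limited form. As written, analysis 3 would check, screen and possibly adjust for active-disease time under the name of remission, and its Charlson index would give metastatic solid cancer no points. The first contradiction is explicit in the SAP. The second follows from a missing line and rests on the extracted list being complete.

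The reach is one conditional sensitivity analysis and, for Charlson, the baseline description as well. The size of any change in the adjusted odds ratio cannot be computed from the SAP. It is zero if illness duration and variable no. 3 both enter linearly, and otherwise depends on which covariates are selected. The overlap figures of 0.89 to 0.98 rest on assumed distributions. That metastatic patients are few is also an assumption. The correction should be made before database freeze because it is nearly free, not because the primary conclusion depends on it.

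**What to change.** 1. In the variables of interest, define duration of remission as the CRF p10 months divided by 12, and use that variable in analysis 3. If active-disease duration was intended, keep the subtraction, state the division by 12, and rename the variable both in row no. 3 and in the list of analysis 3.
2. In row no. 8, add a scoring line for metastatic solid cancer from the version of the Charlson score that the sponsor adopts, with points not below those for localised cancer, and cite that version.

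The cost is two derivation lines, plus one label in the list of analysis 3 if the variable is renamed, made under the SAP's own amendment procedure. No new data are needed, since both items are already in the CRF.
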